Hypothesis and Aims: We hypothesize that anti-obesity pharmacotherapy (vs placebo) will have an effect on weight loss among patients using an activity tracker as part of a lifestyle intervention. Thus, we aimed to study in a randomized, double blinded, placebo-control, 1-year, single-center trial the effect of Phentermine-topiramate ER (Anti-obesity Pharmacotherapy) vs placebo among patients with obesity using a wearable activity tracker as part of standard lifestyle intervention.

Methods/Study Design: We propose a randomized, single-center trial in 80 patients with obesity to study the Effect of an anti-Obesity Medication Phentermine-Topiramate Extended Release vs placebo among patients using a wearable activity tracker in weight loss and obesity related comorbidities in 12 months. All the participants will receive a wearable activity tracker with a Bluetooth scale as part of an intense lifestyle intervention (14 visits total with dietitians, physicians and behavioral therapists (or 6 visits and at least one contact per week virtually with wellness coach) and they will be randomized 1:1 to placebo or Phentermine-topiramate ER (Dosing of 3.75/23 mg daily for 15 days, increased to 7.5/46 mg daily). Participants will be randomized according to a computer generated randomization schedule generated by the study statistician's office and submitted to the Mayo Clinic CTSA research pharmacy. Allocation will be concealed. Study endpoints: a) Primary: Total body weight loss at 3 months among the groups; and b) secondary: Total body weight loss at 6, 9 and 12 months among the groups; number of steps (average per week at 3, 6, 9 and 12 months among the groups); calories tracked: number times recorded, calories per day (average per week at 3, 6, 9 and 12 months among the groups), number of exercise sessions (average per week at 3, 6, 9 and 12 months among the groups); hours/week using app/tracker (average per week at 3, 6, 9 and 12 months among the groups); weight loss difference in clinic vs. Bluetooth scale (weight loss difference 3, 6, 9 and 12 months); Quality of life SF36 (at 3, 6, 9 and 12 months among the groups); improvement in obesity-related comorbidities (diabetes/HbA1c, hypertension/SBP-DBP, hyperlipidemia/TC-LDL-HDL-Tg, Sleep apnea/CPAP, Joint Disease/pain).

Protocol

Effect of a Consumer-Based Wearable Activity Tracker in Combination with an Anti-Obesity Pharmacotherapy in Obesity: Randomized, Placebo-Control, 1-Year, Single-Center Trial

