13. Visit 7-9 monthfollow up
14. Remote visit-10 month
15. Remote visit-11 month
16. Visit 8-12 month End of study

				Months												
				1		2	3	4	5	6	7	8	9	10	11	12
Study Procedures	Visit 1 Screening	Visit 2 Baseline Studies	Visit 3 Counseling and Randomization	Remote Study Visit 2-Week (+/- 3 days)	Visit 4 4-Week (+/- 3 days)	Remote Study Visits	Visit 5	Remote Study Visits	Remote Study Visits	Visit 6	Remote Study Visits	Remote Study Visits	Visit 7	Remote Study Visits	Remote Study Visits	Visit 8
Informed Consent	X															
Medical History and Physical Examination	X															
Pregnancy Test	X*	X*	X*		X*		X*			X*			X*			X*
Vital Signs	X	X	X	X	X		X			X			X			X
Metabolic Studies		X														X****
Blood Collection		X					X**			X**			X**			X**
Medication Diary																
Dispense medication			X			X			X		X		X			
Medication Reconciliation			X			X			X		X		X			

Wearable Tracker and Digital Wellness Devices Given			X													
Randomization and Medication/Placebo Prescription			X													
Behavioral Questionnaires	X***	X ^a														X
Stool Sample		X														
Adverse Event Assessment				X	X	X	X	X	X	X	X	X	X	X	X	X
Review VitalCare Measurements /pregnancy test results				X	X	X	X	X	X	X	X	X	X	X	X	X
Lifestyle Intervention Review			X													
Home Urine Pregnancy Tests Given					X		X			X			X			

* may be done up to 48 hours prior to visit.

**fasting blood draw only (basic metabolic panel, lipid panel, HbA1C, hsCRP, plasma hormones and proteomics.

***HADS, AUDIT-C and Eating disorders questionnaire only

**** Body composition, fasting blood for basic metabolic panel, lipid panel, HbA1C, hsCRP, metabolomics, plasma hormones and proteinomics

^a All questionnaires except HADS, AUDIT-C and Eating disorders questionnaire

^b Visit window for visits 5, 6, 7, 8 and all remote visit is +/- 5 days.

Randomization and Allocation

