All participants will complete the baseline assessment at the Mayo Clinic after an 8-hour fasting period, and the following characteristics will be measured at baseline: Fasting blood collection, body composition, resting energy expenditure, gastric emptying with meal for breakfast, behavioral questionnaires, exercise capacity and performance and buffet meal test for lunch. Blood will be collected for assessment of metabolomic biomarkers, gastrointestinal hormones, DNA (blood). Stool samples for microbiome and bile acid. Participants will return to the CRTU to pick up medication based on the randomization, the wearable activity tracker and the digital wellness devices.

If participants have already completed the baseline assessment at the Mayo Clinic within the last 3 years, those participants will not need to complete the full baseline assessment. Participants will complete the baseline assessment at the Mayo Clinic after an 8-hour fasting period again, but only the following characteristics will be measured at baseline: Fasting blood collection and body composition. Blood will be collected for assessment of metabolomics biomarkers, gastrointestinal hormones, DNA (blood). Stool samples for microbiome and bile acid. Participants will return to the CRTU to pick up medication based on the randomization, the wearable activity tracker, and the digital wellness devices.

Methods of metabolic studies

- a) Body composition will be measured by DEXA (dual energy x-ray absorptiometry).
- b) Resting energy expenditure was assessed by indirect calorimetry with a ventilated hood (Parvo Medics, Sandy, UT).
- c) Gastric emptying (GE) of solids by scintigraphy: The primary endpoint is gastric half-emptying time (GE $t_{1/2}$) [3, 33, 34]. Images will be acquired at 0, 60, 120 and 240 minutes following the normal clinical gastric emptying testing protocol without a push meal.
- d) Appetite (hunger level) by visual analog score fasting and after standard meal for GE and prior to the Satiation test [3].
- e) Satiation will be measure by *ad-libitum* buffet meal to measure total caloric intake and macronutrient distribution in the chosen food. Satiation will be reported in calories consumed at fullness (satiation) [3].
- f) Satiety by visual analog score postprandial after standard meal for GE and after to the *ad-libitum* buffet meal test for every 30 minutes for 2 hours [3]. Satiety will be measured in length of time of fullness.

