- c) Eating Disorders Questionnaire - The Questionnaire on Eating and Weight Patterns-Revised (34), is a valid measure of screening for eating disorders which has been used in several national multi-site field trials. Respondents are classified as binge eating disorder, purging bulimia nervosa, non-purging bulimia nervosa, or anorexia nervosa. We have used this instrument to screen for eating disorders in obese populations.
- d) Three Factor eating questionnaire is 21-item questionnaire, validated, to assess for emotional eating disorders and food cravings.
- e) Physical Activity Level - The four-item Physical Activity Stages of Change Questionnaire (38) will be utilized to assess the physical activity level of participants. Mayo Clinic investigators, led by co-investigator [name], have used these items to explore the relationship between quality of life and physical activity in an NCI-funded study on long-term lung cancer survivors (38).
- f) Exercise behavior- The Exercise Regulations Questionnaire (BREQ-3)(39) and its subsequent modifications have become the most widely used measures of the continuum of behavioural regulation in exercise psychology research. It has been used either as a multidimensional instrument giving separate scores for each subscale, or as a unidimensional index of the *degree* of self-determination.
- g) SF-12v2- a common questionnaire used to measure quality of life
- h) STOP-BANG- questionnaire used to screen for obstructive sleep apnea
- i) WOMAC- questionnaire used to assess osteoarthritis of the knee and hip

Intense Lifestyle Intervention and Behavioral Treatment

All the participants will meet the multidisciplinary team which consists of an Obesity Expert physician, registered dietitian nutritionist as standard of care in our clinical practice. All participants will be guided to 1) Nutrition: Reduce dietary intake below that required for energy balance by consuming 1200calories per day for women and 1400calories per day for men; 2) Physical Activity: reach the goal of 10,000 steps or more per day; 3) Exercise: reach the goal of 150 minutes or more of cardiovascular exercise/week; 4) Limit consumption of liquid calories (i.e. sodas, juices, alcohol, etc.). All participants will receive a personal fitness tracker, where their activity and calories will be tracked. This information will be given in a booklet format.

Wearable tracker:

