Urine pregnancy testing will be done at visits 1, 2, 3, 4, 5, 6, and 8 for women of child bearing potential (WOCBP). Subjects who are WOCBP will be given urine pregnancy test kits (QuickVue+ hCG Combo Test (Quidel Corporation) or similar) along with instructions to complete at home. Subjects will be instructed to complete these home pregnancy test kits and report the results during the remote study visits with the study team. If a subject has a positive urine pregnancy test result at any time the subject will be withdrawn from the study and instructed to stop use of the study medication/placebo immediately. The subject will be given a referral to their primary care provider.

Statistical Considerations

Primary endpoint: Total body weight loss at 3 months

Secondary endpoints:

- Total body weight loss at 6, 9 and 12 months
- number of steps (average per week at 3, 6, 9 and 12 months)
- calories tracked: number times recorded, calories per day (average per week at 3, 6, 9 and 12 months)
- number of exercise sessions (average per week at 3, 6, 9 and 12 months)

- hours/week using app/tracker (average per week at 3, 6, 9 and 12 months)
- weight loss difference in clinic vs. Bluetooth scale (weight loss difference 3, 6, 9 and 12 months)
- Quality of life SF36 (at 3, 6, 9 and 12 months)
- improvement in obesity-related comorbidities (diabetes/HbA1c, hypertension/SBP-DBP, hyperlipidemia/TC-LDL-HDL-Tg, Sleep apnea/CPAP, Joint Disease/pain)

Design: We propose a randomized, double-blinded, placebo-controlled trial of 80 participants with obesity to compare effects of Phentermine-topiramate ER vs placebo in weight loss with 1 year follow up.

Sample size assessment and power calculation: In our recent pilot study [with Liraglutide 3.0 mg vs. placebo], the standard deviation (SD) for the overall weight change (pre-post at 12 weeks) observed was 2.8kg [32] and observed weight loss in the control/placebo group was 6.1kg.

Conservatively assuming a standard deviation of 3kg within groups,

Difference to Detect (kg) – reflects greater weight loss in active arm vs placebo	Sample Size per group	TOTAL Sample Size	With 10% dropout at 3 months	With 15% dropout at 3 months	With 20% dropout at 3 months
1kg (ex: 7.1 vs 6.1)	143	286	318	338	358
1.5kg	64	128	142	152	160
2 kg	37	74	82	88	94

Actual power is anticipated to be higher when accounting for baseline weight using Analysis of Covariance (ANCOVA) methods.

Statistical Analysis:

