The primary analysis will be conducted under intention to treat (ITT) principles. Since study drug is administered double-blind, all subjects taking at least one dose of study drug will be included in analyses.

Primary endpoint: The primary endpoint is weight at 3 months (12 week visit), compared between groups using Analysis of Covariance (ANCOVA), adjusted for baseline weight. Subjects without follow up (dropouts) will have values imputed using multiple imputation. This approach assumes the distribution of missing data is random after conditioning on observed data in the imputation process. A secondary approach will consider complete case data, though this does not generally adhere to ITT principles.

Weight is recorded longitudinally at several post-baseline timepoints. A secondary analysis will model these longitudinal data using linear mixed effects models, adjusted for baseline weight. Additional adjustment variables will be included based on *a priori* determination by investigators that such variables may be associated with the dropout process. Thus, any dropout is assumed Missing At Random as a function of observed data. Time after randomization will be included as a discrete ordinal variable corresponding to the visit number. The primary comparison is a time by treatment group interaction, so that contrasts of the variables in the model will allow estimation of the treatment effect at each visit.

An interim analysis will be performed after 50% of subjects have completed their 3 month visit. This will allow the study team to review data quality and check assumptions related to the power calculation (including the standard deviation

above). Investigators will remain blinded to group comparisons and while investigators have no intention of stopping the study early (regardless of interim results), the analysis at study completion will be conservatively adjusted using the O'Brien-Fleming boundary (two-sided significance level of 0.0492).

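### The quality-of-life endpoint is SF-36 at months 3, 6, 9 and 12, but the plan lists only SF-12v2 and schedules one post-baseline questionnaire visit, at month 12

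*Combined protocol and SAP*

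**What the plan says.** **Endpoint.** Statistical Considerations, Secondary endpoints, lists "Quality of life SF36 (at 3, 6, 9 and 12 months". The Abstract and Methods/Study Design carry the same endpoint: "Quality of life SF36 (at 3, 6, 9 and 12 months among the groups".

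**Instrument list.** Item h under Methods of metabolic studies gives nine self-administered questionnaires, a to i. Item g reads "SF-12v2- a common questionnaire used to measure quality of life". SF-36 is not among the nine.

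**Schedule.** The study flowsheet has no separate quality-of-life row. Its Behavioral Questionnaires row is marked at Visit 1, with the footnote "HADS, AUDIT-C and Eating disorders questionnaire only"; at Visit 2, with the footnote "All questionnaires except HADS, AUDIT-C and Eating disorders questionnaire"; and at Visit 8, with no footnote.

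**Analysis.** For weight, the Statistical Analysis section plans a longitudinal mixed model with a time-by-treatment interaction, in which "contrasts of the variables in the model will allow estimation of the treatment effect at each visit". It then says secondary endpoints are handled in a similar way. Quality of life is to be collected at study visits and compared between groups with linear mixed models. Neither the form nor the visits are named.

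**Baseline.** Under Baseline Characteristic studies, the full baseline includes "gastric emptying with meal for breakfast, behavioral questionnaires, exercise capacity and performance and buffet meal test for lunch". For participants assessed at the site within the previous 3 years, "only the following characteristics will be measured at baseline: Fasting blood collection and body composition".

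**The concern.** The endpoint text and the operational text disagree on both the form and the time of collection. Site staff work from the schedule. If they do so here, the trial cannot report quality of life at three of its four stated times, and visits that have passed cannot be recovered.

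If the conflict is left until analysis, someone must choose the instrument and the reporting times after the data exist. Pre-specification is meant to prevent exactly that.

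A smaller question is whether participants with the reduced baseline have a Visit 2 score to adjust for.

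**Working it through.** The plan gives no numerical figure to reproduce here. The check compares the sections and counts marks.

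**Instrument**

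| Place | Form named |
|---|---|
| Abstract | SF-36 |
| Methods/Study Design | SF-36 |
| Secondary endpoints | SF-36 |
| Questionnaire list, items a to i | SF-12v2 |
| Statistical Analysis | none named |

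SF-36 is the endpoint in all three places where the endpoint is stated, and it is listed for collection nowhere.

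**Timing**

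The visit list places Visits 5, 6, 7 and 8 at months 3, 6, 9 and 12.

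| Time | In endpoint | Questionnaire mark in schedule |
|---|---|---|
| Screening (Visit 1) | no | yes, three screening forms only |
| Baseline (Visit 2) | no | yes, all other forms |
| Month 3 (Visit 5) | yes | none |
| Month 6 (Visit 6) | yes | none |
| Month 9 (Visit 7) | yes | none |
| Month 12 (Visit 8) | yes | yes, forms not specified |

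Stated post-baseline times: 4. Marked: 1. Unmarked: 4 - 1 = 3.

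**Could the table have been misread from the PDF?** The questionnaire row has its full width of 17 cells (the row label plus 16 visits). The Vital Signs row, read in the same way, falls on all eight in-person visits and the 2-week remote visit. Six rows carry marks at all of Visits 5, 6 and 7: pregnancy test, vital signs, blood collection, adverse events, VitalCare review and home pregnancy kits. So the table can show activity at those visits.

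Not every row is tidy. Dispense medication and Medication Reconciliation fall partly on remote months, and Medication Diary is empty. The conclusion therefore rests on the count of marks, not on their alignment. There are three marks, and the footnotes fix two of them before randomization: 3 - 2 = 1 possible post-baseline collection. A shifted column cannot raise that number.

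**Consequence for the model.** With one post-baseline score per participant, post-baseline time has a single level, so a time-by-treatment interaction cannot be fitted. The analysis reduces to a month-12 comparison adjusted for baseline. Multiple imputation does not help: a score observed in nobody at months 3, 6 and 9 leaves no data on which to build the imputation.

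**Baseline.** The Visit 2 footnote calls for the remaining questionnaires with no exemption. The reduced-baseline paragraph omits them. The documents do not say how many participants have the reduced baseline or how a missing baseline score is handled, so any loss of precision cannot be calculated.

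**The case against.** The strongest reply is that the schedule is the weaker source. Three statements of the endpoint agree on four times. The analysis text refers to study visits in the plural and plans mixed models, which fits repeated collection better than a single one. In-person Visits 5 to 8 fall at exactly the stated months.

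The table also looks incomplete elsewhere. The Medication Diary row is empty. The visit list puts body composition at Visit 5, yet the Metabolic Studies row is blank there. Marks may simply have been left out, in which case the intended collection is four times and the harm does not arise.

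This stands as a reason to state the consequence conditionally. It does not remove the contradiction, because a site given this protocol has no instruction to hand out a quality-of-life form at months 3, 6 or 9. Nor does it touch the instrument conflict, which nothing in the documents resolves.

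Two lesser replies have some force:

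- In a row where restricted marks carry footnotes, an unqualified mark at Visit 8 would ordinarily mean every form, including SF-12v2. A footnote there is a clarification, not a correction.
- The reduced baseline applies to people who completed the baseline assessment within 3 years, so an older score may exist. The word limiting that baseline may also not be strict, since stool samples are mentioned straight afterwards. The baseline point is therefore minor.

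**Conclusion.** The concern holds and should be fixed. The instrument conflict is unconditional: the form named in the endpoint is listed for collection at 0 of the 4 stated times.

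The loss of months 3, 6 and 9 assumes that the schedule, and not the endpoint text, governs what is done. The documents do not settle which applies. If forms are in fact collected at every in-person visit, only the instrument conflict remains.

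This is one of eight secondary endpoint items, and none is adjusted for multiplicity. The baseline discrepancy is real as written but is not quantified, and the conclusion does not depend on it.

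**What to change.** 1. Use one instrument name in the Abstract, Methods/Study Design, Secondary endpoints, questionnaire list and Statistical Analysis (for example SF-12v2, which is already in the list).
2. Make the times agree, by one of two routes:
   - (a) Mark that form in the schedule at Visits 5, 6 and 7.
   - (b) Restate the endpoint as month 12 only, compared between groups with adjustment for the Visit 2 score.
3. Add a Visit 8 footnote naming the quality-of-life form.
4. State that every participant, including those with the reduced baseline, completes the form at Visit 2.

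**Cost.** Both routes need a protocol amendment, since Randomization and Allocation has the Institutional Review Board approve the protocol.

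- Route (a) adds one self-completed form at three visits that already take place: at most 80 x 3 = 240 forms. Using the outer dropout rates in the sample-size table (10% and 20% by month 3) and assuming no later loss, it adds 80 x 0.90 x 3 = 216 or 80 x 0.80 x 3 = 192. It cannot recover visits already completed.
- Route (b) adds no data collection but is an endpoint change that gives up three of the four time points.
- The baseline item costs one sentence, and one form at Visit 2 for each participant with the reduced baseline.

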A computer generated randomization schedule generated by the study statistician's office will be submitted to the Mayo Clinic CCaTS Research Pharmacy. Randomization will be based on guiding pharmacotherapy or placebo. Allocations will be concealed. This study will be blinded until data are transmitted to the statistician for data lock. All subjects will be given a verbal explanation of the study, provided time to read and study the written consent form and its information, given opportunities to ask questions and a copy of the consent form. Participants will be informed of their right to withdraw from the study at any time without prejudice to their clinical management now or in the future. Consent will be sought by one of the medical doctor investigators or the study coordinator, and consent will be documented by the participant's signature on the consent form. Mayo's Institutional Review Board will approve the process and protocol. All the members of multidisciplinary team for weight management (i.e. physicians, coordinators, clinical assistants, registered dietitians will remain blinded).

If unblinding is needed for subject safety the Principal Investigator or a Co-Investigator will contact a research Pharmacist or the research pharmacy manager and provide documentation of reason for study unblinding and the subject will be withdrawn from the study. The study team will document and report the reason for unblinding as required by the Mayo Clinic IRB.

Selection Participants

We plan to study a cohort of 80 patients with obesity ($BMI > 30 \text{ kg/m}^2$). Participants will be recruited from the Mayo Clinic Weight Management and Nutrition Clinic, media advertising, classified ads, and existing databases of patients with obesity, including the phenome registry (Mayo Clinic IRB number [REDACTED]), the Mayo Clinic biobank and the right-10k cohort.

Inclusion criteria

- a) Adults with obesity ($BMI > 30 \text{ Kg/m}^2$); these will be otherwise healthy individuals with no unstable psychiatric disease and controlled comorbidities or other diseases.
- b) Age: 18-75 years.
- c) Gender: Men or women. Women of childbearing potential will have negative pregnancy tests within 48 hours of enrollment.
- d) Women of childbearing potential must agree to use a method of effective contraception during study participation.

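### The final two-sided level of 0.0492 does not follow from an O'Brien-Fleming boundary with one look at 50%, which gives 0.0480 at an overall alpha of 0.05 (0.0490 with Lan-DeMets spending)

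*Combined protocol and SAP*

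**What the plan says.** The Statistical Analysis section sets the timing of a single interim look: "An interim analysis will be performed after 50% of subjects have completed their 3 month visit". Its purpose is to review data quality and to check the assumptions behind the power calculation, including the standard deviation. The section adds that "Investigators will remain blinded to group comparisons" and that "investigators have no intention of stopping the study early (regardless of interim results"). Even so, "the analysis at study completion will be conservatively adjusted using the O'Brien-Fleming boundary", and the same sentence prints the resulting level: "boundary (two-sided significance level of 0.0492").

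Under Randomization and Allocation the plan says: "This study will be blinded until data are transmitted to the statistician for data lock".

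The plan gives no overall alpha, no interim critical value and no spending function. The paragraph headed "Sample size assessment and power calculation" gives 143, 64 and 37 per group for differences of 1, 1.5 and 2 kg, "Conservatively assuming a standard deviation of 3kg within groups", but states neither alpha nor power.

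**The concern.** The plan supplies all that is needed to compute the final level except the overall alpha: the boundary, the number of looks and the timing. With the usual overall 0.05, the computed level differs from the printed one. The figure is the decision threshold of the primary test. A statistician who implements the named method would use 0.0480 (or 0.0490), and one who follows the printed number would use 0.0492. The two would disagree on any final p value in between, and the plan does not say which half of its sentence governs.

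**Working it through.** **Inputs.** From the Statistical Analysis section: one look, information fraction t = 0.50, O'Brien-Fleming boundary, final two-sided level 0.0492. From Statistical Considerations: SD 3 kg; 143, 64 and 37 per group. From the study design: 80 participants allocated 1:1, so 40 per arm. Assumed: overall two-sided alpha 0.05 and, for the sample-size table only, 80% power.

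**Step 1. Does the plan's own table fit 0.05?** Sample size per group for a two-sample t test, SD 3 kg, 80% power:

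| Two-sided alpha | 1 kg | 1.5 kg | 2 kg |
|---|---|---|---|
| 0.05 | 143 | 64 | 37 |
| 0.0492 | 143 | 65 | 37 |
| 0.0490 | 144 | 65 | 37 |
| 0.0480 | 145 | 65 | 37 |

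The 0.05 row reproduces the printed table. This supports 0.05 but does not prove it, because the power is not stated. The same 143, 64 and 37 also arise at alpha 0.0513 with about 80.3% power and at 0.0480 with about 79.5% power.

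**Step 2. The two-look calculation.** Under the null, the interim and final statistics Z1 and Z2 are bivariate normal with correlation √t = √0.5 = 0.7071. The critical values c1 and c2 must satisfy

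P(|Z1| ≥ c1 or |Z2| ≥ c2) = 0.05.

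*O'Brien-Fleming.* The shape is c1 = c2/√t. Solving gives c2 = 1.9774 and c1 = 1.9774/0.7071 = 2.797. The interim level is 0.0052 and the final level is 2 × [1 − Φ(1.9774)] = **0.0480**.

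*Lan-DeMets O'Brien-Fleming-type spending, 0.025 per side.* Alpha spent by t = 0.5 is 4 × [1 − Φ(2.2414/√0.5)] = 0.0031 in total, so c1 = 2.963. Solving for the rest gives c2 = 1.9686 and a final level of **0.0490**.

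**Step 3. Working back from 0.0492.** A two-sided 0.0492 is z = 1.9669.

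- With the O'Brien-Fleming shape, c1 = 1.9669/0.7071 = 2.782, and the overall alpha of the two-look design is 0.0513.
- With the Lan-DeMets interim value of 2.963, the overall alpha is 0.0502.
- Holding overall alpha at 0.05, a final level of 0.0492 arises with a look at about 40% information (O'Brien-Fleming) or about 48% (Lan-DeMets). The plan says 50%.

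**Step 4. What is at stake as planned.** With no stopping at the interim, the final test is a single test at 0.0492 and its type I error is 0.0492, below 0.05.

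**Step 5. Power.** For 2 kg, SD 3 kg, 40 per arm, t test, no dropout:

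| Final level | Power |
|---|---|
| 0.05 | 83.76% |
| 0.0492 | 83.58% |
| 0.0490 | 83.54% |
| 0.0480 | 83.31% |

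Moving from 0.0492 to 0.0480 costs 83.58 − 83.31 = 0.27 points. Moving to 0.0490 costs 0.04 points.

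**The case against.** The strongest reply is that nothing goes wrong in operation. The threshold is fixed in advance, anyone can apply it without deriving it, and with no interim stopping any level at or below 0.05 is valid. Calling the adjustment conservative is then accurate. All of this stands, and it is why the point is minor. It does not make the attribution right: the plan says the number comes from a named boundary, and at 50% it does not.

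A second reply is that 0.0492 may be an O'Brien-Fleming constant of limited precision, since the overall alpha it implies, 0.0513, is only 0.0013 from 0.05. The documents do not show how the figure was obtained, so this cannot be excluded. Whatever its origin, exact calculation gives 0.0480, and the plan prints four decimals.

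A third reply is that overall 0.05 is itself inferred. That is also fair. The sample-size table pins alpha down to about 0.0495 to 0.0502 only if power is exactly 80%, which the plan does not say.

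A reader might go further and infer that the primary test is inflated to 0.0513. The documents do not support that. The figure applies only if the interim could end the trial for efficacy at the matching O'Brien-Fleming value. The plan disclaims early stopping, and investigators stay blinded to group comparisons.

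**Conclusion.** The concern holds as a small error in a stated number. Given one look at 50% and an overall two-sided alpha of 0.05, the final level is 0.0480 for O'Brien-Fleming, a difference of 0.0012 from the printed figure. It is 0.0490 for Lan-DeMets O'Brien-Fleming-type spending, a difference of 0.0002. Neither the validity of the primary test nor the sample size is in question. The printed level and the named method lead to different conclusions only for a final p value between 0.0480 (or 0.0490) and 0.0492.

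The conclusion rests on the overall alpha being 0.05, which the plan should confirm, and on the information fraction being the 50% that it states.

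**What to change.** State the overall two-sided alpha as 0.05, then take one of two routes before unblinding.

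1. **Keep the O'Brien-Fleming adjustment.** Replace 0.0492 with 0.0480, or name Lan-DeMets O'Brien-Fleming-type spending and use 0.0490. The cost is about 0.3 points of power or less for 2 kg with 40 per arm.
2. **Drop the adjustment.** State that the interim makes no group comparison, cannot stop the trial and spends no alpha; remove the reference to the boundary; and test at 0.05. Relative to 0.0492 this gains 83.76 − 83.58 = 0.18 points of power. It fits the purpose that the plan gives for the interim.

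Either route takes one or two sentences in the Statistical Analysis section. There is no operational cost, and the 37 per group for 2 kg is unchanged at all of these levels (assuming 80% power).
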